4.1.3.3 CDAI Remission and Clinical Remission Every 12 Weeks

The percentage of patients in CDAI remission or clinical remission as defined in the Efficacy Derivations Section 1.3.1 will be summarized for each OLE visit for patients who entered Study GA29145. All OLE visits will be summarized until a minimum of 20 evaluable patients overall remain within the analysis (i.e., an evaluable patient either reached the visit or could have reached the visit if they had remained within the OLE).

Population: Patients who enroll into Part 1 of Study GA29145.

Baseline: The original baseline value from the parent study will be used to calculate remission, where applicable.

Sub-groups:

- Table outputs: All patients overall, split by aTNF exposure status and by OLE Day 1 CDAI remission or clinical remission status, as appropriate.
- Figure outputs: All patients overall and split by OLE Day 1 CDAI remission or clinical remission status.

Analysis 1 - Hybrid LOCF

Missing data: If patients who remain in Study GA29145 at the specified visit are missing data then LOCF will be used to impute. For visits where patients are non-evaluable (i.e. it is not possible for them to have reached the specified visit at the time of the clinical cut-off date) they will be removed from the analysis.

Intercurrent Events: Using the composite strategy in the case where patients have withdrawn from the Study GA29145, they will be set to non-responders for all visits where they are evaluable. This excludes patients who withdrew from study drug with reason being stated as “study terminated by sponsor” after 15th February 2022.

Analysis 2 - As Observed

Missing data: If a patient has missing data at a visit, they will be removed from the analysis and no imputation will be performed.

Intercurrent events: No imputation will be performed for treatment withdrawals

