(TNF-IR) with moderately to severely active CD in the combined Phase III, randomized, placebo-controlled induction and maintenance studies, Study GA29144.

Patients who experience disease worsening that is confirmed at Week 10 in the Induction Phase of Study GA29144 will have the option of enrolling in Part 1 (OLE) of Study GA29145 between and including Weeks 10 and 14 of the Induction Phase. Patients who are not eligible for the Maintenance Phase may also have the option to enroll in Part 1 (OLE) of Study GA29145, if eligible. During the Maintenance Phase in Study GA29144, patients will be able to withdraw and enter Part 1 (OLE) if they experience a clinical relapse (as defined in Section 4.1.1).

Study GA29144 patients who experience disease progression or lack of response while assigned to placebo during either the Induction or Maintenance Phase are expected to benefit most from participation in Part 1 (OLE) of Study GA29145. Patients who experienced disease progression or lack of response while assigned to etrolizumab in Study GA29144 may also experience treatment benefit by participating in Part 1 (OLE) depending on severity of disease and available treatment options, which include anticipated treatment benefit from rescue medication. Consequently, eligible patients from Study GA29144 are encouraged to enroll in Part 1 (OLE) to receive open-label etrolizumab with rescue medications at the discretion of the investigator, including the use of concomitant immunosuppressant therapy.

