4.1.1 Inclusion Criteria

Part 1 (OLE)

- Patients who were previously enrolled in Study GA29144 and experienced any of the following:

Disease worsening in the Induction Phase of Study GA29144, defined as a CDAI score at Week 10 or later in the Induction Phase being greater than the patient's baseline (Week 0) score

Not eligible for the Maintenance Phase in Study GA29144

Completed the Week 14 visit in Study GA29144 and could not subsequently enter the Maintenance Phase, because the sample size for the Maintenance Phase has been achieved

A clinical relapse during the Maintenance Phase of Study GA29144, defined as meeting at least one of the following criteria on two consecutive visits (may include unscheduled visits), with at least one of the two consecutive CDAI scores ≥ 220 :

CDAI score \geq the baseline (Week 0) score

CDAI score ≥ 100 points higher than the Week 14 score

Completed the Maintenance Phase including the Week 66 or Week 74 clinic visit in Study GA29144

- Ability and willingness to provide written informed consent and comply with the requirements of the OLE-SM protocol.
- For women who are not postmenopausal (at least 12 months of non-therapy-induced amenorrhea) or surgically sterile (absence of ovaries and/or uterus): agreement to remain abstinent or to use a highly effective method of contraception (e.g., combined oral contraceptive pill or transdermal patch, spermicide and barrier [condoms], intrauterine device, implants for contraception, injections for contraception [with prolonged release], hormonal vaginal device, sterilization, or surgical tubal ligation) during the treatment period and for at least 24 weeks after the last dose of study drug (see [Appendix 4](#)).

Abstinence is acceptable only if it is in line with the preferred and usual lifestyle of the patient. Periodic abstinence (e.g., calendar, ovulation, symptothermal, or postovulation methods) and withdrawal are not acceptable methods of contraception.

- For men: agreement to remain abstinent or to use a condom, as well as not donate sperm, during the treatment period and for at least 24 weeks after the last dose of study drug

Abstinence is acceptable only if it is in line with the preferred and usual lifestyle of the patient. Periodic abstinence (e.g., calendar, ovulation, symptothermal, or postovulation methods) and withdrawal are not acceptable methods of contraception.

PART 2 (SM)

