4.1 GENERAL CONSIDERATIONS

4.1.1 Analysis of Study Conduct

The number of patients who discontinued early (early discontinuation of OLE treatment or early termination from the study) or completed the study will be tabulated.

Reasons for early discontinuation of treatment or early termination from the study will be listed and summarized. Any eligibility criteria exceptions and other major protocol deviations will also be summarized.

Since Part 1 (OLE) of GA29145 was terminated by the Sponsor on 15th February 2022, no patients are expected to reach treatment completion. As a result of this, the end of Part 1 (OLE) of GA29145 is defined from the last dose date in GA29145 on 15th May 2022.

In summary, the following will be summarised for GA29145 Part 1 (OLE):

- Analysis populations
- Patient disposition
- Study treatment completion/discontinuation
- Study completion/discontinuation
- Major protocol deviations
- Exposure

Treatment Labels

For the OLE population, the only treatment arm to be summarized is:

Group	Patients Included
OLE Etrolizumab	Patients in the OLE population who receive at least one dose of etrolizumab in Study GA29145 Part 1 (OLE)

All tables should be presented by treatment group only.

Part 1 (OLE) Day 1

OLE Study Day 1 is defined as the day patient has the first receipt of study drug in GA29145 Part 1 (OLE).

Baseline

Baseline is defined as the last available assessment prior to first receipt of study drug in the Induction Phase of the parent study, GA29144.

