4.1.3 Primary Efficacy Analysis

To evaluate the efficacy of etrolizumab during long-term open-label treatment, efficacy will be summarized within the population of patients who enroll into the Study GA29145. Both endoscopic improvement and clinical remission will be summarized in two separate analyses. Due to the open-label nature of the study, no treatment comparisons will be made.

Concerning missing data and treatment withdrawal imputation, there will be 3 strategies employed, described below.

Hybrid LOCF

Within this strategy, at each visit only patients who had the possibility of reaching the visit will be considered in the analysis for that specified visit. Patients will be deemed evaluable at a visit if it was possible for them to have reached this visit based on their enrollment date and the date of the closure of Part 1 of the study.

- Patients for whom it is not possible to have reached the visit at the time of the clinical cut off are termed non-evaluable and will not be included in the analysis at that visit.
- For evaluable patients with missing data, Last Observation Carried Forward (LOCF) will be used from their most recent available data.

- For evaluable patients who previously withdrew from treatment, they will be imputed as a non-responder until their maximum hypothetical visit (i.e., the maximum visit that they could have attended if they had remained within the study).
 - For visits after a patient's maximum hypothetical evaluable visit, they will be removed from the analysis.

As Observed

Within this analysis only the available data at each visit will be summarized. No imputation will be performed for missing data or treatment withdrawals.

Non-Responder

Within this strategy, at each visit only patients who had the possibility of reaching the visit will be considered in the analysis for that specified visit. Patients will be deemed evaluable at a visit if it was possible for them to have reached this visit based on their enrollment date and the date of the closure of Part 1 of the study.

- Patients for whom it is not possible to have reached the visit at the time of the clinical cut off are termed non-evaluable and will not be included in the analysis at that visit.
- Evaluable patients with missing data will be set as a non-responder.

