- For evaluable patients who previously withdrew from treatment, they will be imputed as a non-responder until their maximum hypothetical visit (i.e., the maximum visit that they could have attended if they had remained within the program).
 - For visits after a patient's maximum hypothetical evaluable visit, they will be removed from the analysis.

Maximum Hypothetical Evaluable Visit

A patient's maximum hypothetical study day (i.e., the maximum visit that they could have attended if they had remained within the study) is calculated as follows:

Maximum hypothetical study day = (15th May 2022 - Patient's Day 1 OLE enrollment date)

For the hybrid LOCF analysis and non-responder analyses, this will impute patients who have withdrawn as a non-responder until the 15th May 2022, which was the latest day of dosing reported in the closure of the study announcement. This excludes patients who withdrew from study drug with reason being stated as "study terminated by sponsor" after 15th February 2022, these patients will not be imputed as non-responders and will be considered 'treatment completers' for the efficacy analysis with data included "as observed".

Simple Endoscopic Score for Crohn's disease (SES-CD) score: Handling of Partially Available Segments

Note that in the OLE study GA29145, no central adjudication took place and therefore only a local score will be available for the Week 108 assessment. This differs from Study GA29144, which utilized central adjudication and up to 3 readers provided a score. To overcome differences in reader availability between studies the following approach will be used:

Baseline score will utilize data from all available readers with adjudication applied to determine the final total SES-CD score. This aligns with the original Day 1 Baseline score in study GA29144 and ensures that the central readers are retained in the Baseline score derivation, as reported in the CSR analysis.

The determination of segment availability will use the Local reader only for both the baseline and post-baseline time points, as follows:

- any segment(s) missing by the local reader at baseline will not be considered in the Week 108 visit total SES-CD total score calculation

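### The overall by-visit remission curve in SAP 4.1.3.3 mixes change within patients with change in who is evaluable, and the planned split by OLE Day 1 remission handles this only in part

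*SAP*

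**What the plan says.** **Denominator.** SAP 4.1.3 sets evaluability separately for each time point: "Patients will be deemed evaluable at a visit if it was possible for them to have reached this visit based on their enrollment date". Closure of Part 1 is the other determinant. The maximum hypothetical study day is 15 May 2022 minus OLE Day 1. SAP 4.1.3.3 removes patients from a visit when "it is not possible for them to have reached the specified visit at the time of the clinical cut-off date". The same section sets how far the display runs, with a floor of 20: "All OLE visits will be summarized until a minimum of 20 evaluable patients overall remain within the analysis".

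**Withdrawals.** In the Hybrid LOCF analysis, withdrawn patients stay in: "they will be set to non-responders for all visits where they are evaluable". The exception is patients who stop after 15 February 2022 because the sponsor terminated the study; SAP 4.1.3 includes them as observed. The As Observed analysis drops any patient without data at the visit.

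**Splits.** Tables are planned overall, by anti-TNF exposure and by OLE Day 1 remission status. Figures are planned overall and by Day 1 remission status. No split by entry route and no fixed-cohort curve is planned.

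**Entry routes.** Protocol 1.3.3 and 4.1.1 let patients in at different points of the parent study:
- disease worsening, at parent Weeks 10 to 14;
- ineligibility for Maintenance;
- relapse during Maintenance;
- completion of Maintenance, at Week 66 or 74;
- completion of Week 14 by patients who "could not subsequently enter the Maintenance Phase, because the sample size for the Maintenance Phase has been achieved".

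**The concern.** Long-term efficacy is a stated Part 1 objective. With no control arm and no test, the shape of the remission curve is the main by-visit evidence on it. A reader will take a falling line as loss of effect and a flat one as effect maintained.

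That reading needs the same patients, or the same mix of patients, along the line. Here the set thins by entry date. For two patients randomised in the parent study on the same day, a Maintenance completer starts the OLE 52 to 60 weeks after a Week 14 entrant (66 − 14 = 52; 74 − 14 = 60). The route for Week 14 completers shut out of Maintenance does not exist until Maintenance has filled. The earliest OLE entrants, who alone populate the last visits, can therefore come only from the induction routes.

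If remission differs by route, the curve moves as the mix moves. The protocol expects outcome to depend on prior course, since patients with progression or "lack of response while assigned to placebo during either the Induction or Maintenance Phase are expected to benefit most".

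**Working it through.** The plan states no expected remission rate, route count or accrual pattern for this curve, so there is no figure of its own to reproduce. The check applies the SAP's evaluability rule while holding each patient's remission status fixed, so that all movement comes from the denominator.

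**From the documents:** cut-off 15 May 2022; entry at parent Week 14 (route A) or Week 66/74 (route B); 12-week visits; display floor of 20; N = 1150, which is the protocol's maximum rather than an expected number.

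**Assumed:** uniform parent accrual over R weeks (200 to 260); cut-off G weeks after the last parent randomisation (90 to 120); route A share 50% to 60%; remission rates as shown below.

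**Formulas.** With lag L (52 or 60 weeks) between the routes:
- n_A(t) = N·w_A·min(1, (R + G − 14 − t)/R)
- n_B(t) = N·w_B·min(1, (R + G − 14 − L − t)/R), both set to 0 if negative
- p(t) = [n_A(t)·p_A + n_B(t)·p_B] / [n_A(t) + n_B(t)]

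**Main scenario:** R = 260, G = 120, L = 60, shares 60/40, p_A = 20%, p_B = 60%. Then n_A = 690·min(1, (366 − t)/260) and n_B = 460·min(1, (306 − t)/260).

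| Week | n_A | n_B | Total | Overall remission |
|---|---|---|---|---|
| 0 to 36 | 690 | 460 | 1150 | 36.0% |
| 108 | 684.7 | 350.3 | 1035 | 33.5% |
| 240 | 334.4 | 116.8 | 451 | 30.4% |
| 312 | 143.3 | 0 | 143 | 20.0% |
| 348 (last shown) | 47.8 | 0 | 48 | 20.0% |

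The total fall is 16 points with nobody changing; 36.0 − 33.5 = 2.5 points of it come by Week 108.

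**Other assumptions** (start to end):
- 30% and 50%, shares 60/40: 0.6×30 + 0.4×50 = 38% to 30%, a fall of 8 points.
- 20% and 60%, shares 50/50: 40% to 20%, a fall of 20 points.
- 60% and 20%, shares 60/40: 44% to 60%, a rise of 16 points.
- The first change appears between Week 24 and Week 60, once the shortest potential follow-up is passed.

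**Planned Day 1 split.** With no change since Day 1, its lines are flat at 100% and 0%. Now let Day 1 non-remitters gain remission at different rates by route. In the main scenario they number 690×0.8 = 552 (A) and 460×0.4 = 184 (B). With gains of 25% (A) and 10% (B), the line starts at (138 + 18.4)/736 = 21.2% at Week 12. It is 21.9% at Week 108 and 25.0% at Week 348. With the gains reversed, it runs from 13.8% to 10.0%.

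**Fixed cohorts.** In the main scenario the 1035 patients evaluable at Week 108 give 33.5% at every visit to Week 108. The 451 evaluable at Week 240 give 30.4% at every visit to Week 240. Neither line moves.

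**Boundary and floor.** 15 May 2022 minus 108 weeks (756 days) is 19 April 2020; later OLE entrants are not evaluable at Week 108. At 20 patients, 10/20 has an exact 95% interval of 27% to 73%.

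**The case against.** The strongest reply is that the SAP already splits by OLE Day 1 remission, in tables and figures. The line for Day 1 remitters is the natural display of maintained effect, and it is flat when nothing changes. That stands, and it reduces the problem. It does not remove it: the curve is drawn because status may change after Day 1, and a stratum drifts if the routes differ in that change. The drift in the example is under 4 points.

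Other points also stand. The analysis is descriptive, the report is synoptic with limited efficacy data, and the SAP does not say the overall curve will support a durability claim. Ordinary dropout does not shift the Hybrid LOCF set. The Week 108 endoscopic non-responder analysis uses a single evaluable set, though at one time point. Movement by Week 108 may be small.

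Three stronger readings are tempting and unsupported:
- **That the analysis cannot show whether efficacy is kept.** Early visits use a constant set, and the Day 1 remitter line carries real information.
- **That better-prognosis routes enter late, so a fall is expected.** No document gives route-specific rates or dates. Induction routes stay open while the parent study runs induction, and Week 14 completers may enrol only if eligible. The expectation that placebo failures benefit most points the other way for early entrants.
- **That the SAP bars subgroup tables.** "All tables should be presented by treatment group only" stands under the single-arm treatment labels, and 4.1.3.3 itself specifies subgroups.

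**Conclusion.** The concern holds for the overall Hybrid LOCF curve. Its denominator depends on entry date, entry date is tied to entry route, and no planned by-visit output separates a change in mix from a change in patients.

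The illustrative size is a fall of 8 to 20 points or a rise of 16 over the full displayed range, with much less by Week 108 in the main scenario. These figures rest on the assumed accrual, route shares and rates. From the documents alone, neither size nor direction can be fixed, and there is no artefact if remission does not differ by route. The planned Day 1 split leaves a smaller residual, which arises only if routes differ in change after Day 1.

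This is a weakness in interpretability that is cheap to repair; no test or error rate is at stake.

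**What to change.** In SAP 4.1.3.3:

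1. Add a fixed-cohort version of the Hybrid LOCF curve, overall and by OLE Day 1 remission status, restricted to patients evaluable at Week 108 and shown at every visit from Day 1 to Week 108.
2. Add a second fixed cohort for a later common visit at which at least 20 patients remain. Choose that visit from enrolment dates alone and name it in the SAP. It matters because most of the movement can come after Week 108.
3. Base any statement on maintenance of effect over time on the fixed-cohort curves. Keep the all-evaluable curve as a description.
4. Under the overall curve, show the number evaluable at each visit by entry route. The documents describe no route field; derive it from the last parent-study visit and the eligibility data.
5. State how fixed-cohort members who stopped because of the sponsor's termination count at visits they did not attend, since the SAP takes them as observed.

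The cohorts need only the enrolment date that the SAP already uses, so the work is SAP wording and reruns of an existing program. The costs are fewer patients per line, a few extra outputs, and some derivation for route. A full outcome split by route and parent treatment is not requested, because its late cells could be very small.

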During Part 1 (OLE), patients who have worsening CD may receive corticosteroid concomitantly (IV, oral, or topical) at the discretion of the investigator (see Section 4.3.1). Patients may continue immunosuppressant therapy (i.e., AZA, 6-MP, or MTX) with dose changes or initiate immunosuppressant therapy, at the discretion of the investigator (see Section 4.3.1). Any patient taking a prohibited therapy (described in Section 4.3.2) must withdraw from Part 1 (OLE), discontinue etrolizumab, and complete the 12-week safety follow-up, and then enter Part 2 (SM).

Upon completion of the 12-week safety follow-up, patients will enter Part 2 (SM) of the study, which will consist of 92 weeks of extended PML monitoring. See Figure 1 and Figure 2 for schemas of the study and see Section 3.1.3.

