5.1.2 Risks Associated with Worsening of Crohn's Disease

The worsening of CD may result in the use of rescue medications. In severe cases, worsening of CD may lead to hospitalization or require surgery.

At any time during the study, patients who have worsening of their CD will be permitted to receive additional therapy with corticosteroids (IV, oral, or topical). Addition of or increases in doses of immunosuppressants (i.e., AZA, 6-MP, or MTX) will also be allowed if clinically indicated by the Principal Investigator.

Rescue therapy with anti-TNF agents (including TNF inhibitor biosimilars), cyclosporine, tacrolimus, sirolimus, MMF, natalizumab, vedolizumab, anti-adhesion agents, rituximab, other lymphocyte depleting agents (except AZA and 6-MP, or equivalent), or other biological or investigational therapeutics will not be allowed in conjunction with etrolizumab because of the level of immunosuppression anticipated with the use of these agents. Patients who receive any of these prohibited rescue medications are not to receive further treatment with etrolizumab, are to complete the 12-week safety follow-up, and should then enter into Part 2 (SM) of the study.

See Section 4.4.2 and Appendix 1 for the schedule of assessments to be performed in the event of worsening of CD, which may lead to an unscheduled visit.

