1. INTRODUCTION

The analyses described in this Statistical Analysis Plan (SAP) will supersede those specified in Protocol GA29145 for the purposes of reporting.

The purpose of this document is to describe the analyses for reporting out Part 1 of the Open-Label-Extension Safety Monitoring (OLE-SM) study for GA29145. This SAP will solely focus on reporting data collected during Part 1 (OLE) of GA29145.

This OLE-SM study is composed of two parts:

1. Part 1 is the OLE for eligible patients, during which etrolizumab, 105 mg SC, will be administered Q4W followed by a 12-week safety follow-up post-treatment.
2. Part 2 is the 92-week PML SM for all patients, during which no etrolizumab will be administered.

[figure not shown]
Patients who are enrolled in Part 1 (OLE) should participate in Part 2 (SM).

There may be patients from Study GA29144 who are ineligible for or choose not to participate in Part 1 (OLE) who will be asked to directly enroll in Part 2 (SM).

Key characteristics of the GA29145 OLE-SM are provided in [Table 1](#). Treatment arms and rollover of patients from induction/maintenance to GA29145 OLE-SM from parent CD studies are depicted in [Figure 1](#) and [Figure 2](#).

[figure not shown]
The maximum number of patients enrolled in GA29145 OLE-SM is approximately 1150 (i.e., all patients enrolled in Study GA29144). No formal sample size calculations were performed.

Figure 1 Study Schema for Part 1 (Open-Label Extension; OLE) of the OLE-SM Study

OLE=open-label extension; OLE-SM=open-label extension—safety monitoring; Q4W=every 4 weeks; Q12W=every 12 weeks; SC=subcutaneous.

Figure 2 Study Schema for Part 2 (Safety Monitoring; SM) of the OLE-SM Study

OLE=open-label extension; OLE-SM=open-label extension—safety monitoring; PML=progressive multifocal leukoencephalopathy; ~Q24W=approximately every 24 weeks.

Table 1 Key Characteristics of GA29145 OLE-SM in CD (Juniper)

Study	GA29145 (Phase III)	
Treatment (Number Exposed)	Open-label etrolizumab 105 mg SC Q4W (n= up to ~1150)	
Study Phases	OLE up to 10 years from FPI 12-week safety follow-up 92-week PML monitoring	
Key Eligibility Criteria	Part 1 (OLE)	Part 2 (SM)**

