- any segments(s) available at baseline that are not available at Week 108 will result in a non-responder status for the patient for endoscopic improvement/remission. For continuous data the patient's baseline segment score will be carried forward (BOCF) to impute the Week 104 segment score when calculating the total SES-CD score.

4.1.3.1 Endoscopic Improvement and Remission at Week 108

As endoscopy data is only collected at a common time point of Week 108 during the OLE Study GA29145, the endpoints of endoscopic improvement and endoscopic remission will be summarized only at this time point. These endpoints will be examined overall and separated by their previous endoscopic improvement status at their latest visit prior to enrollment into GA29145 i.e., at the parent study's (GA29144) Week 14 or Week 66.

The handling of patients with partially available segments is detailed in Section [4.1.3](#), this is not considered as true missing data.

Population: All patients who enrolled into Part 1 of the OLE Study GA29145.

Baseline: The original baseline value from the parent study will be used to calculate improvement.

Sub-groups:

- All patients overall and split by prior endoscopic improvement status and their prior aTNF exposure status.

Analysis 1 - Non-Responder

Missing data: Patients who are non-evaluable at Week 108 (i.e., could not have reached the maximum visit if they had remained within the program as detailed in Section 4.1.3) will be removed from the analysis. Patients who remain in Study GA29145 but are missing endoscopy scores (i.e., the assessment was not done) will be imputed as non-responders within the analysis, as LOCF is not appropriate when endoscopy data is not collected routinely.

Intercurrent events: Patients who withdraw during Study GA29145 will be set to non-responders using the composite strategy if they could have reached OLE Week 108 at the time of the clinical cut-off date had they not withdrawn from treatment. This excludes patients who withdrew from study drug on or after 15th February 2022.

Analysis 2 - As Observed

Missing data: If a patient has missing data at a visit, they will be removed from the analysis and no imputation will be performed.

Intercurrent events: No imputation will be performed for treatment withdrawals

4.1.3.2 Simple Endoscopic Score for Crohn's disease (SES-CD) score at Week 108

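### Hybrid LOCF for remission has two non-response triggers, leaving treatment (SAP 4.1.3) and leaving the study (SAP 4.1.3.3), which disagree for patients off etrolizumab, still in GA29145 and last scored in remission

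*SAP*

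**What the plan says.** SAP 4.1.3 sets out the Hybrid LOCF strategy. Its trigger for non-response is leaving treatment: "For evaluable patients who previously withdrew from treatment, they will be imputed as a non-responder until their maximum hypothetical visit".

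SAP 4.1.3.3 applies the strategy by name, as Analysis 1, to CDAI remission and clinical remission every 12 weeks. Its trigger is leaving the study: "Using the composite strategy in the case where patients have withdrawn from the Study GA29145, they will be set to non-responders". Its missing-data branch uses the same status: "If patients who remain in Study GA29145 at the specified visit are missing data then LOCF will be used to impute".

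The documents do not treat the two events as one. SAP 4.1.1 lists "early discontinuation of OLE treatment or early termination from the study" as alternatives, and the protocol gives withdrawal from the study (4.5.1.1) and discontinuation of study drug (4.5.2) separate sections.

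On what GA29145 includes, the SAP Introduction says "This OLE-SM study is composed of two parts": the OLE with its 12-week safety follow-up, and the 92-week PML monitoring. Protocol 3.2.1 ends the study only when the last patient completes that monitoring. Protocol 4.4.3 routes patients who stop treatment for any reason through an early withdrawal visit and the follow-up into Part 2. Protocol 4.5.2 does the same for the listed mandatory stops. Protocol 5.1.2 says of patients given prohibited rescue that they "are to complete the 12-week safety follow-up, and should then enter into Part 2 (SM) of the study".

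**The concern.** A patient who has stopped etrolizumab but is in the safety follow-up or Part 2 has left treatment without leaving GA29145. Neither period has a scheduled CDAI or diary assessment (Protocol Appendices 2 and 3), so remission data will be missing at each later 12-week visit for which the patient still counts as evaluable. SAP 4.1.3 sends this patient to non-response. The literal text of 4.1.3.3 sends the same patient to LOCF.

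The trigger matters here because the missing-data branch is LOCF. A programmer who follows 4.1.3.3 as written would keep counting a last score of remission as etrolizumab remission after the drug has stopped, in both remission outcomes and in every subgroup reported from Analysis 1. The error could run in one direction only, upwards.

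**Working it through.** The plan gives no remission rate, withdrawal rate or power figure, so there is no planned number to reproduce. The check sets the two rules side by side and then works out what can be said about size.

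**Step 1. Case check.** Take a scheduled 12-week visit for which the patient is evaluable, after etrolizumab has stopped.

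| Patient's situation | SAP 4.1.3 | SAP 4.1.3.3, literal |
|---|---|---|
| In follow-up or Part 2, last score in remission | Non-responder | Remission (LOCF) |
| In follow-up or Part 2, last score not in remission | Non-responder | Non-responder (LOCF) |
| Left GA29145 without completing Part 2 | Non-responder | Non-responder |
| Completed Part 2, visit still evaluable | Non-responder | No rule: neither remaining nor withdrawn |
| Stopped after 15 February 2022, reason given as sponsor termination | Exempt, as observed | Exempt |

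The rules give opposite results in the first row only, and 4.1.3.3 is silent in the fourth.

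**Step 2. Duration.** Safety follow-up plus Part 2 is 12 + 92 = 104 weeks (Protocol Appendix 3, footnote a). 104 / 12 = 8.67, so at most 8 or 9 scheduled visits per patient fall in this span. Fewer apply when the 15 May 2022 limit in SAP 4.1.3 comes sooner, or when the patient does not enter Part 2.

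**Step 3. Size at one visit.** Let d be the share of evaluable patients who are off etrolizumab but still in GA29145, and q the share of those whose last score was remission. Then

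literal 4.1.3.3 rate − 4.1.3 rate = d × q ≥ 0.

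The documents give neither d nor q. Purely to show how the formula behaves, assume d from 10% to 50% and q from 0% to 40%:

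- q = 0%: 0 points for any d
- d = 10%, q = 10%: 0.10 × 0.10 = 1.0 point
- d = 30%, q = 25%: 0.30 × 0.25 = 7.5 points
- d = 50%, q = 40%: 0.50 × 0.40 = 20 points

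These are not estimates for this trial.

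**Step 4. What the documents do fix.** SAP 4.1.3.3 summarises visits until a minimum of 20 evaluable patients overall remain. At that floor one reclassified patient moves the overall rate by 1/20 = 5 points, and by more within a subgroup, where the denominator is smaller.

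**Step 5. Does the same wording matter elsewhere?** SAP 4.1.3.1 (endoscopic endpoints, Non-Responder analysis) also mixes withdrawal during the study with withdrawal from treatment: it speaks of patients "if they could have reached OLE Week 108 at the time of the clinical cut-off date had they not withdrawn from treatment". Its missing-data branch is also non-response, so either trigger gives the same result. The As Observed analyses impute nothing and are unaffected.

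**The case against.** The strongest reply is that *Study GA29145* in this SAP is shorthand for the OLE. The SAP covers Part 1 only. SAP 4.1.3.3 describes evaluability as having stayed within the OLE, words its exception as withdrawal from study drug, and speaks of treatment withdrawals under Analysis 2. An exception about drug withdrawal makes sense only if the main rule is about drug withdrawal. Protocol Appendix 3, footnote a, even counts the 104 weeks from the patient's discontinuation from the study. On that reading, a patient who must withdraw from Part 1 (Protocol 3.1.2) is a non-responder under both sections.

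This stands as evidence of intent, but it does not remove the conflict. Protocol 3.2.1 and footnote b of Appendix 3 place Part 2 inside the study, and Protocol 5.4.1 equates not entering Part 2 with withdrawing consent from the study. The population line of 4.1.3.3 names Part 1 explicitly, so the authors could do so where they meant it. Even under the shorthand, Protocol 4.5.2 puts the 12-week follow-up within Part 1, so a patient in follow-up could still be read as remaining.

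Four stronger readings are tempting, and the documents do not support them:

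- *That the two rules generally give opposite imputations.* They do so only when the carried score is remission. Prohibited rescue is tied to worsening disease (Protocol 5.1.2), so many of those patients may last have been out of remission. Stops for pregnancy, malignancy or hypersensitivity while in remission are the clearer cases.
- *That every such patient contributes 8 or 9 affected visits.* That is a maximum (step 2). Part 2 is expected but not certain, and patients who withdraw consent instead are non-responders under both rules.
- *That scores obtained on prohibited rescue will be carried forward.* This is possible, since the early withdrawal visit may fall up to 30 days after the last dose. But CDAI is taken there only if diary data exist (Appendix 1, footnotes f and h), and nothing shows how often this would occur.
- *That the reported rates are inflated by a known amount.* The documents do not show which rule was programmed, and they give neither share in step 3.

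**Conclusion.** The point holds as a contradiction in wording. SAP 4.1.3.3 is wrong as written, because followed literally it departs from the strategy it names. The departure affects patients who are off etrolizumab, still in GA29145 and last scored in remission; for those who have completed Part 2 the section gives no rule. The literal rate is equal to or higher than the 4.1.3 rate at every visit. How much higher cannot be derived from the documents; the only anchored figure is 5 points per reclassified patient at the 20-patient floor.

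The conclusion rests on reading the study as Parts 1 and 2 together, as Protocol 3.2.1 does. Treatment withdrawal is very probably what the authors meant, and if the programs already follow 4.1.3 no result changes. The analysis is descriptive, so no test or error rate is at stake.

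**What to change.** In SAP 4.1.3.3, Analysis 1:

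- In the intercurrent-event rule, make the trigger *withdrawn from study drug* in place of withdrawal from Study GA29145.
- In the missing-data rule, apply LOCF to patients *who have not withdrawn from study drug* in place of those who remain in Study GA29145.
- Keep the exception for sponsor termination as it stands.
- Add one sentence: being in the 12-week safety follow-up or Part 2, or having completed Part 2, does not change non-responder status at visits for which the patient is evaluable.

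For consistency, use the same trigger wording in 4.1.3.1, where the result does not change.

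The cost is wording only. No new data, endpoint or output is needed, and no rule for stopping treatment is touched. The reason for stopping study drug is already recorded on the eCRF (Protocol 4.5.2), and SAP 4.1.1 already tabulates treatment discontinuation. If the programs follow the literal 4.1.3.3, they need a re-run and the Hybrid LOCF rates may fall.
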